Feasibility. Assessment completion was 85%-100% for all outcomes. Participants exercised with the app an average of  $2.4\pm1.7$  times per week and attended 35 / 40 monthly discussions (88%). Participants were queried on each non-exercise day about their barriers to exercise, and app malfunction was reported as a barrier <1% of the time. CGM data capture was  $92.5\pm7.2\%$  during baseline and  $88.3\pm9.8\%$  during weeks 9-10, with 95% of timepoints meeting literature standard  $\geq 75\%^{60}$ . Accelerometer wear time at baseline met the literature standard of  $\geq 10$  hours per day on  $6.7\pm0.6$  out of 7 days, with all participants above literature standard of  $\geq 4$  days per week, and accelerometer data at follow-up are pending analysis. Participants completed a median of 98% (IQR 88%, 100%) of the 84 possible mobile diaries, with 90% meeting literature standard  $\geq 70\%$ .

Safety. There were no episodes of ketoacidosis or severe hypoglycemia. Episodes of mild hypoglycemia were recorded on mobile diaries and reviewed by Drs. [name], [name], and [name] biweekly for safety concerns.

Acceptability. The overall intervention rating was moderate (3.4±0.9 out of 5). Participants rated the monthly feedback and coaching discussions most acceptable of all components (4.4±0.8 out of 5) but requested more frequent feedback and coaching sessions. The elements designed for more frequent touchpoints were rated somewhat lower (exercise videos 3.8±0.9, text-based exercise coach 3.2±0.8, daily diaries 2.2±0.6), *indicating need for more automated and frequent support as planned in the current study*.

Preliminary Efficacy. Participants increased their exercise from a median of 4 (IQR 0, 41) to 64 (20, 129) minutes per week (d= 0.71). Body mass index increased (d= 0.57). Systolic blood pressure (d= -0.45), HbA1c (d= -0.42), and mean sensor BG (d= -0.41) tended to slightly decrease while total daily insulin (d= 0.09) was not different. In summary, the intervention was safe and showed promising efficacy, *supporting virtually delivered exercise guidance if it can be delivered more intensively and sustainably*.

August 13, 2024 Version #7

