### 3.2 Hypothesis

### **PRIMARY**

*Hypothesis 1-1*: The mobile intervention will meet standards of feasibility.

Hypothesis 1-2: The mobile intervention will generate positive user feedback and suggested refinements.

Hypothesis 1-3-1: The data will verify that a prior-constructed machine-learning algorithm that predicted exercise adherence in a prior dataset will continue to do so with acceptable accuracy (receiver-operator characteristic AUC .80, or precision-recall AUC .80 if <20% of days are lapses).

Hypothesis 1-3-2: The data will verify that prior detected patterns in blood glucose safety hazards will continue to appear with expected frequency (≥1 of the above patterns occurring in ≥80% of person-weeks).

Hypothesis 1-3-3: The data will verify that small or greater (d≥0.1) changes in blood glucose resulting from exercise are detectable by a Bayesian model.

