The exported data include firstly exercise adherence, by tracking usage of exercise guidance (videos or guided outdoor walking). Fitbit heart rate readings verify exercise timing, duration, and intensity. The Borg Rating of Perceived Exertion prompt captures intensity for non-aerobic exercises such as weightlifting (Appendix 8c). The extracted data also include contextual variables that may predict vulnerability to missing exercise: 1) 24hr blood glucose derived from interstitial vales sampled every 5min by the CGM and expressed by consensus metrics (coefficient of variation, mean, % time >180, 70-180, <70mg/dL). 2) Fear of hypoglycemia the previous night and coming day (Appendix 8a). 3) Sleep Quality the previous night from self-report (Appendix 8a) and Fitbit (sleep time overestimation ~10%); 4) Competing demands and exercise plan (Appendix 8a); 5) Weather; (temperature, humidity, windchill) captured using GPS location and the National Weather Service API; 6) Day of the week (weekday vs. weekend). 7) Insulin dosing (including entered carbohydrates) from the participant's device (InPen, Tandem, Omnipod, or Medtronic). 8) Physical activity outside of exercise videos; captured by the proprietary Fitbit algorithm (intensity classification accuracy 85%, step counts ±3%;).

The above markers of individual context, day of the week, and between-participant characteristics, including demographics and clinical characteristics that can impede exercise (body composition, mobility limitations), will be exported from GlucoseZone to our Yale Secure Server for processing by our machine-learning code. The code is programmed to identify predictors of exercise "lapse," defined as the 3rd missed day of the week or 2nd consecutive missed day given that the goal is 150 min/week spread over ≥5 days. Thereafter, when the code detects these predictors, the research assistant running the code will signals the exercise coach to edit then send a specific encouragement message. E.g., if high blood glucose variability is a vulnerable state predictor, the just-in-time message meeting its occurrence would read: "Sometimes blood glucose can go up and down. You can still be active using the strategies you and your provider have discussed." This encouragement does not extend to suggestions of specific exercises or managing low blood glucose.

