The mathematical basis of the code is a binary classification model of exercise lapse using Python scikit-learn package v. 0.19.098, including random forests and gradient boosted tree ensembles (such as XgBoost99). We have completed analyses that train the model at the group level which was aim 2 of our prior protocol (HIC #2000025992). Briefly, we collected data on blood glucose, insulin dosing, fear of hypoglycemia, sleep, illness, and exercise occurrence. We ran two types of machine learning – random forest and dense neural network -- to predict exercise lapses (i.e., days without exercise) based upon prior days' blood glucose, fear of hypoglycemia, sleep, and illness. The data were randomly split where 80% of persondays were used to train the model and the other 20% were used to test the model. The present study will use the random forest model which had the highest accuracy (79%). Its sensitivity to predict exercise lapses was 83% and specificity was 71%. A **confidential** draft of the full manuscript describing the development is included (Appendix 20). These accuracy metrics, while limited, are better than the non-Al alternative of sending an encouraging message every day without any attempt to select for the most vulnerable days. Doing so can lead the participants to develop alarm fatigue and silence the notifications.

These models have been pruned to reduce the complexity of the final classifiers and avoid overfitting the training data. This group-level model (Appendix 9a) will be the starting point for training a person-level model for each participant via supervised transfer learning methods during the present study to give the participant tailored prompts. This strategy mitigates the shortness of the timeframe (4 weeks) to train each

August 13, 2024 Version #7

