If needed, separate models for subgroups can be established in the subsequent beta version of the app. Third, model-generated messages will be validated against the human-edited messages that are released to participants during the study (c.f. Sect 6.1.1, tool #2). Models are evaluated by the number of lapses required to train person-level models to reach acceptable accuracy (receiver-operator characteristic AUC .80, or precision-recall AUC .80 if <20% of days are lapses), thus estimating a "learning window" before users can expect adaptive feedback. Third,

**Hypothesis 1-3-2. Detect Exercise Safety Hazards.** Tabulate the occurrence of the common safety hazards (Table 3) and report them by frequency statistics.

**Hypothesis 1-3-3. Assessing Exercise Glycemic Response.** The mathematical basis of the R-code is our Bayesian time series model. Briefly, it compares CGM metrics over each 1-4 week period against a counterfactual predicted based upon the CGM during the 1-4 weeks before the period and the covariates over the 1-4 week period. The full formalism and an example of this analysis is available in our manuscript. The advantage over linear modeling frameworks is the flexibility to evaluate the intervention's effect strength at all points in the intervention period. If p-values do not reach significance ( $\alpha$ =.05) then the next version of the app will extend the length of the testing window before providing feedback, though even 1 week of CGM data at minimal adherence (70%) yields k=1,411 observations resulting in 96% power to detect a small effect size (d≥0.10) at  $\alpha$ =.05. The maximum window of 4 weeks was chosen as a typical minimal frequency of health coaching sessions for long-term maintenance of lifestyle change.

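### The plan carries two definitions of an exercise lapse; under the Tool #2 definition, ROC AUC .80 can be reached from missed-day counts alone, and no benchmark is set

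*Combined protocol and SAP*

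**What the plan says.** Section 6.1.1 (Visit 4, Tool #2) gives the label that the code is programmed to predict: the third missed day of the week or the second "consecutive missed day given that the goal is 150 min/week spread over ≥5 days". It does not say whether further missed days in the same week or run also count, or whether the week is fixed or rolling. Of the data passed to the code it says: "The exported data include firstly exercise adherence". Contextual variables such as glucose, fear of hypoglycemia, sleep and weather are listed after that.

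The next paragraph describes the pilot model that is carried forward. It was built to "predict exercise lapses (i.e., days without exercise") from prior days' glucose, fear, sleep and illness, with accuracy 79%, sensitivity 83% and specificity 71%. The only alternative it is compared with is a message every day.

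Section 3.2 sets the bar for Hypothesis 1-3-1: "receiver-operator characteristic AUC .80, or precision-recall AUC .80 if <20% of days are lapses". Section 7.2 repeats the bar for the person-level models: "Models are evaluated by the number of lapses required to train person-level models to reach acceptable accuracy". It also says the trial data will first validate the pilot group-level model. Neither section says which label is scored, which days enter the AUC, or what the model must beat.

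**The concern.** Under the Tool #2 label a day can be a lapse only if yesterday was missed or two days of that week are already missed. On every other day a lapse is impossible, whatever the participant does. That status is known before the day begins to anyone holding the exercise record. An AUC over all days therefore gives credit for separating possible from impossible days, and chance performance is no longer .50.

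Hypothesis 1-3-1 is a primary test of mathematical robustness. The same .80 also defines the learning window that the next app version would use. A pass could reflect the construction of the label. In addition, a model trained on one label could be validated on another without the report showing it.

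**Working it through.** **The plan's own figure.** Accuracy = sensitivity × prevalence + specificity × (1 − prevalence). Section 1.2.1 says "Participants exercised with the app an average of" 2.4±1.7 times per week. With one session per exercise day, the daily miss rate is 1 − 2.4/7 = .657. Then .83 × .657 + .71 × .343 = .545 + .244 = .789, against 79% stated. Solving back, prevalence = (.79 − .71)/(.83 − .71) = .667, or .58 to .75 allowing for rounding. Lapses under the Tool #2 label would be about 21–26% of days (once-only reading) or 51–53% (cumulative reading). The pilot figures thus fit days without exercise, provided the pilot test split had the pilot's exercise rate.

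**The no-skill rule.** Flag a day if a miss on it would be a lapse. Every lapse is flagged, so
- ROC AUC = 1 − P(flagged | no lapse)/2
- precision-recall (PR) AUC = lapse days / flagged days

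**Simulation inputs.** 24 participants (section 7.1), 28 days (four weeks), misses independent from day to day, personal miss rates Beta-distributed to match 2.4±1.7 sessions a week, and fixed weeks.

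- *Once-only reading* (exactly the third weekly or second consecutive miss): 33% of days are flagged and 21% are lapses. Flagged non-lapses are .33 − .21 = .12 of days, and .12/.79 = .152, so AUC = 1 − .152/2 = .924. The simulated value is .926–.927, with 95% range .90–.95. PR AUC = .21/.33 = .64.
- *Cumulative reading* (later misses also count): about three quarters of days are flagged and 53% are lapses. Simulated ROC AUC is .779–.784, with 95% range .74–.83. PR AUC is .73.

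**Full two-branch criterion.**
- Once-only: ROC AUC is at or above .80 in every run. Lapses fall below 20% of days in about 30–35% of runs; the PR branch then applies, and the rule never reached .80 on it. It therefore passes in about 65–70% of trials (for example 1 − .353 = .647). The spread depends on whether sampling variance is removed from the pilot SD.
- Cumulative: lapses never fell below 20% of days, so the ROC branch always applies. The rule passes in about 17–23% of trials.

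**Adding a running personal miss rate, from prior days only.** Multiplying the flag by this rate gives ROC AUC .955 (once-only) and .875 (cumulative), at or above .80 in 100% and 99% of runs. No glucose, fear or sleep data are used.

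**Sensitivity of the yes/no rule.**

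| Setting | Once-only | Cumulative |
|---|---|---|
| One common miss rate, .2 to .9 | .86–.98 | .71–.89 |
| Rolling 7-day week | .93 | .70 |
| Day-to-day correlation .2 | .94 | .80 |
| At-risk days only | .50 | .50 |

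Day of week alone, without the missed-day record, gives about .56–.76 at the pilot rate. Under the pilot label with a common miss rate, the count rule scores .50.

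**The case against.** A reader might infer that a rule with no skill always scores .93 and that AUC .80 therefore cannot verify Hypothesis 1-3-1. The documents do not support that, for four reasons.

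- Hypothesis 1-3-1 and Outcome Variable 1-3-1 speak of predicting exercise adherence with the prior algorithm, and that algorithm's label is days without exercise. If this label is scored, the running-count artefact is absent.
- The figure .93 belongs to the once-only reading. The cumulative reading gives about .78, just under the bar.
- The criterion has a precision-recall branch, and the yes/no rule fails it.
- The plan does not show that the model uses missed-day counts. The predictors listed for the pilot model omit exercise history, and adherence may be exported only as the outcome. The code in Appendix 9a is not reproduced in the document.

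It is also fair to say that past behaviour is a legitimate predictor for a tool that chooses which days to message, and that all-day scoring matches this use.

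These points limit the size of the problem and make it conditional. They do not remove it. Two labels stand in adjacent paragraphs, the analysis section chooses neither, and no benchmark would let a reader see how much of an AUC comes from the missed-day record.

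**Conclusion.** The point holds in conditional form. The definition of a lapse is unresolved between two paragraphs of Tool #2, and section 7.2 does not settle it. If the Tool #2 label is scored on all days, a rule using only missed-day counts has ROC AUC about .93 or .78, depending on the reading, and about .96 or .88 with a running personal miss rate. The yes/no rule meets the full criterion in about 70% of once-only trials, where the remaining trials fall to the PR branch. It does so in about 17% of cumulative trials, where its ROC AUC is usually just short of .80.

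These sizes assume independent days, the pilot rate and spread, one session per exercise day and fixed weeks. The pilot's 2.4 counts app sessions, so the true rate of exercise days may differ. If the model can use the exercise record, reaching ROC AUC .80 under this label does not by itself show that glucose, fear or sleep data predict lapses. Whether the model in fact draws on that record cannot be settled from the documents.

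**What to change.** In sections 3.2 and 7.2:

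1. State one lapse definition for Hypothesis 1-3-1. It should be the one the carried-forward model was trained on, or the difference should be justified. If the Tool #2 definition is kept, say whether later misses count and whether the week is fixed or rolling.
2. If the Tool #2 label is scored, compute the AUC on at-risk days, meaning days on which a miss would be a lapse. The yes/no count rule scores .50 there.
3. Under either label, report the model's ROC and PR AUC beside those of a rule using missed-day history only, with the difference and a participant-level bootstrap interval. The benchmark is needed under the pilot label too, because people who differ in miss rate can be told apart by their own history.
4. Base the conclusion on the gain over that benchmark and not on .80 alone. Requiring the interval to exclude zero would be a confirmatory hurdle for a 24-person pilot, and I would not add it.

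The cost is SAP wording and a few lines of code, with no change to visits or data collection. The downside is that fewer days enter the at-risk AUC, about one third (once-only) or three quarters (cumulative), so the figure will be less favourable and less precise.

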They will also be provided a comprehensive exercise safety orientation which is detailed in Appendix 22a. Briefly, the information includes review of devices, supplies, space, safe glucose ranges and carbohydrate snacking for exercise, reminders from CGM training pertinent to exercise, insulin adjustments around exercise, watching for symptoms, and who to call with concerns. They will be provided and instructed to keep carbohydrate-containing foods and drinks (eg, orange juice, glucose tablets) available to use when indicated by glucose testing or symptoms. In addition, they will be educated regarding the American Diabetes Association guidelines for self-monitoring blood glucose and urine ketones, if indicated, and appropriate adjustments of diet and insulin before, during, and after engaging in exercise. For instance, if blood glucose is less than 90 mg/dL, they can consume 10-20g of fast-acting carbohydrates (eg, 4 oz of orange juice or 3 glucose tablets) and wait to commence with exercise until blood glucose is confirmed to be above 90 mg/dL. If blood glucose is greater

Protocol Number 2000035846

August 13, 2024 Version #7

than 270 mg/dL and not associated with a recent meal, they must check their blood for ketones and avoid exercise if they have ketones ≥1.0 mmol/L.

Participants will be encouraged to be vigilant for symptoms of hypoglycemia during exercise and for the remainder of the day because exercise increases the risk for nocturnal hypoglycemia. The symptoms they will be encouraged to be vigilant for include cold, clammy skin, pallor, difficulty concentrating, shakiness, lack of coordination, irritability, hostility, and poor behavior, a staggering gait, fatigue, nervousness, excessive hunger, headache, blurred vision and dizziness, and abdominal pain or nausea. In these instances, they will be advised to refrain from exercise while checking blood glucose.

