Participants will be monitored for exercise-associated events (hypo- and hyperglycemia, diabetic ketoacidosis, other health risks) as detailed in the Data and Safety Monitoring Plan (Sect 8.7). In brief, a research staff member will daily review each participant's CGM data, fingerstick glucose tests, ketone tests, exercise start times, and diary records of hypoglycemia and other clinical events (see Data and Safety Monitoring Plan "Tracking" section) each of the first 14 days of the trial for each participant. Instances of severe hypoglycemia, diabetic ketoacidosis, a missed ketone test, or other clinical event will result in immediate discontinuation of exercise until a physician has alerted the participant and the participant's primary diabetes care provider to the issue and developed a prevention strategy, consulting with the primary diabetes care provider as needed. For instances of a missed test, physician contact can be replaced initially by research assistant contact to query symptoms and troubleshoot testing procedures, followed by physician contact if symptoms were present.

The principal investigator [name] and a study physician (Drs. [name] or [name]) will review the above data plus carbohydrate and insulin dosing around exercise, every 2 weeks during the clinical trial. Participants exhibiting patterns confirmed by the physician to be indicative of problematic exercise-induced hypo- or hyperglycemia will be alerted to the issue and referred to their diabetes care provider for follow-up (all patients will submit provider information to the study team at study start). [name] will join at least every other occurrence of these meetings (i.e., at least every 4 weeks) and provide a second review of [name] medical management decisions. Participants will be trained in allowing their provider to access their CGM data. Mild hypoglycemia will not be exclusionary since such individuals are in high need of exercise intervention. Any day-to-day decisions about clinical care, including adjustment of insulin dosing or CGM target ranges will be made by the participant's provider, not the study physicians. Clinical providers will not monitor CGM in real-time.

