All participants participate in routine follow-up, consisting of quarterly visits to the clinic and 24-hour access to nurse and/or physician consultation. It is not anticipated that any of the data collection procedures or the intervention will cause any adverse effects. Nonetheless, the participants will continue to receive routine medical and nursing care throughout the study period, and intervention for adverse effects will be available.

These protocols have been utilized by Drs. [name], [name], and [name] over four prior exercise clinical trials among youth and adults with T1D that had no instances of severe hypoglycemia or diabetic ketoacidosis (HIC #s 1605017843, 2000025992, 2000030105, 2000033736).

**Hyperglycemia:** There is a risk of hyperglycemia due to exercise from factors such as counterregulatory hormone response releasing glucose into the blood.

See above regarding blood glucose testing, blood glucose monitoring review by research staff, Drs. [name], [name], [name], and routine clinical support. Regarding hyperglycemia

August 13, 2024 Version #7

specifically, participants will be encouraged to be vigilant before, during, and after exercise for signs or symptoms of hyperglycemia such as dry mouth, headache, heaviness, pressure behind the eyes, or unusual increase in thirst. They will be advised in these instances to reassess their blood glucose. If blood glucose is greater than 270 mg/dL and not associated with a recent meal, they should check their blood for ketones and avoid exercise if they have ketones ≥1.0 mmol/L.

**Severe hypoglycemia and hyperglycemia:** There is a risk of severe hypoglycemia or hyperglycemia due to exercise.

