Severe hypoglycemia will be defined as any blood glucose level resulting in symptoms which require outside intervention to control (including but not limited to confusion and loss of coordination). Severe hyperglycemia will be defined as blood glucose >500mg/dL, presence of urine ketones or other signs and symptoms of diabetic ketoacidosis (including but not limited to weakness and fatigue, confusion, shortness of breath). Patients will be asked to contact emergency services should these events occur. Specifically, Yale-affiliated patients with T1D have access to a 24-hour hotline with access to nurse and/or physician advice or can choose to call 911. Non-Yale-affiliated patients will be asked to call 911 or contact their providers' after-hours staff (all patients will submit provider information to the study team at study start). The study team will be notified of the event within 24 hours via daily diaries; moreover all participants will have the PI's direct contact information should they choose to contact him earlier by phone or email. Our team will then notify the patient's primary diabetes provider (if not already notified) and all study-related exercise will be suspended until patient receives further advice from their diabetes provider regarding next steps which may include modified exercise routines or suspension of the study altogether. All serious adverse events such as severe hypoglycemia and hyperglycemia will be reported to the PI verbally within 24 hours of study staff being notified and to university's IRB committee in writing within 5 business days. In the case of >1 episode of severe hypoglycemia or 1 episode of diabetic ketoacidosis not closely related to pump site failure, the participant will be removed from the study and referred to their diabetes care provider for follow-up.

**Exercise-related injuries:** Exercise may cause muscle soreness/pain, muscle strain, cardiovascular events, and tiredness during or after the activity.

The probability and magnitude of such injuries varies based upon factors such as the individual participant's fitness level and the difficulty of the exercise routines. Our previous pilot studies (sect. 1.2) had no injuries or muscle strains. The American Heart Association Scientific Statement notes that the frequency of exercise-related out-of-hospital cardiac arrest among the general population ages 35-90yr was measured at 3.0 per 100,000 person-years.

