A, Based on this blood glucose data, it may be a good idea to review the recommendations from your healthcare professional about how you would adjust your food intake or insulin dosing around exercise. If you do not remember, it would be a good idea to reach out. B, If your blood sugar is high (more than 270 mg/dL) before starting exercise, check your blood or urine for ketones. If you test positive for ketones, avoid vigorous activity. If you do not have ketones in your blood or urine and you feel well, it should be fine to exercise.

Tool #4: Health outcome feedback regarding the causal impact of exercise upon blood glucose (Appendix 18). The GlucoseZone cloud will draw CGM metrics (coefficient of variation, mean, % time >180, 70-180, <70mg/dL) and covariates (insulin-on-board, carbohydrates self-reported into insulin device, exercise metrics including video selected and Fitbit minutes / heart rate / distance / calories / sleep / activity at sub-exercise intensity). The app organizes these data on a dashboard accessible to Yale staff. A Yale staff member exports the contents onto the Yale Secure Server weekly and enters them into our Bayesian R-code (Appendix 9b). The EP reviews the results and accompanying visualizations documenting a positive, neutral, or negative effect of exercise once per 1-4 weeks as insights are generated. The EP will message the client by encrypted emailed pdf relaying the most representative results and/or visualizations and any recommended adjustments by interpretating and applying exercise guidelines (e.g., "You have done purely resistance exercise for the past 28 days, and it has had the causal impact of increasing blood glucose time above target range. Consider more aerobic exercise.") If these EP's recommendations indicate repeating certain videos, they will accordingly appear on the home-screen the following week.

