# **Tracking**

A. Daily monitoring during first 2 weeks for ketoacidosis, severe hypoglycemia, and other health risks associated with exercise:

We will detect any diabetic ketoacidosis or severe hypoglycemia within 24hr and suspend exercise until a personalized preventive strategy can be formed. To achieve this level of monitoring, a research assistant will monitor daily the biometric dashboard which contains Bluetooth-captured glucose, ketones, and exercise start/stop times. Safety signals include any of the following during or within 1hr of exercise: 1) Diabetic ketoacidosis (glucose ≥270 mg/dL + ketones ≥1.0 mmol/L), 2) Possible diabetic ketoacidosis (glucose ≥270 mg/dL and failure to test ketones), and 3) Possible severe hypoglycemia (glucose <55 mg/dL). Research staff will respond to each of these events within 24hr of its occurrence by informing the participant to immediately suspend the exercise program (app account will be suspended) until the participant has been contacted by a study physician. The physician will alert the participant and the participant's primary diabetes care provider to the issue and develop a prevention strategy, consulting with the primary diabetes care provider as needed. The exercise suspension will then be lifted, unless the participant has met the protocol's stoppage criteria (>1 episode of severe hypoglycemia, 1 episode of diabetic ketoacidosis not closely related to pump site failure).

In the event of the "possible" occurrences (#2, #3), physician contact can be replaced initially by research assistant contact to query symptoms. Then, if possible diabetic ketoacidosis is supported by the participant reporting symptoms, or possible severe hypoglycemia is supported by the participant reporting altered mental and/or physical status requiring assistance from another person for recovery, physician contact will be required as in paragraph #1 above.

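### Tip B in the weekly Tool #3 report leaves out the protocol's own rule of no exercise at blood ketones of 1.0 mmol/L or more, or with a positive urine ketone test

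*Combined protocol and SAP*

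**What the plan says.** Section 6.1.1, Tool #3, describes a weekly report that the app's cloud service sends to each participant. Table 3 lists four hazard patterns. The fourth, starting exercise above 270 mg/dL, carries follow-up tip B. Tip B asks for a blood or urine ketone test, then says "If you test positive for ketones, avoid vigorous activity". Its last sentence clears exercise only for someone with no ketones who feels well.

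Elsewhere the protocol says:

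- Section 2.2, Hypoglycemia paragraph, for glucose above 270 mg/dL that a recent meal does not explain: "they must check their blood for ketones and avoid exercise if they have ketones ≥1.0 mmol/L". The Hyperglycemia paragraph repeats this with a softer verb: "they should check their blood for ketones and avoid exercise if they have ketones ≥1.0 mmol/L".
- Section 2.2, Severe hypoglycemia and hyperglycemia: "Severe hyperglycemia will be defined as blood glucose >500mg/dL, presence of urine ketones or other signs and symptoms of diabetic ketoacidosis". Once the team learns of such an event, study exercise stops until the diabetes provider advises.
- Section 8.7, Tracking A, for readings during exercise or in the hour around it. Signal 1 is "Diabetic ketoacidosis (glucose ≥270 mg/dL + ketones ≥1.0 mmol/L" and signal 2 is "Possible diabetic ketoacidosis (glucose ≥270 mg/dL and failure to test ketones". The response is suspension of the exercise program, initially until a study physician has made contact; for signal 2 a research assistant may first ask about symptoms.
- Section 2.2, Hypoglycemia, on missed tests: "Instances of severe hypoglycemia, diabetic ketoacidosis, a missed ketone test, or other clinical event will result in immediate discontinuation of exercise".

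**The concern.** A safety text that participants read should state the protocol's own stop rule. A bar on vigorous activity alone suggests that gentler activity is acceptable. The Tool #1 library offers plenty of that: flexibility, balance and chair-based sessions and guided walks. Participants are also coached to begin with beginner-level classes. For sedentary adults starting out, ruling out only vigorous work may rule out little of what they would do.

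The report looks back over the past week, so tip B can only influence later sessions. If a participant then did a light session with glucose of at least 270 mg/dL and ketones of at least 1.0 mmol/L, that session would fit signal 1 of the monitoring plan.

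The template wording matters more here than for the other tools. The exercise physiologist edits Tool #2 messages and reviews Tool #4 results before they go out. No such check is described for the Tool #3 report.

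**Working it through.** No sample size, power or error rate is involved, so the check sets the texts side by side. Every case has glucose above 270 mg/dL before exercise. Tip B gives no numerical cut-off for a positive test. I read it as any detectable ketones, which its closing sentence about having no ketones supports.

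| Case | Tip B | Section 2.2, blood-ketone rule | Other protocol text | Tip B compared |
|---|---|---|---|---|
| 1. Blood ketones ≥1.0 mmol/L, no recent meal | No vigorous activity | No exercise | Section 8.7 signal 1 if the participant exercises; suspension | Weaker |
| 2. Blood ketones detectable but <1.0 mmol/L | No vigorous activity | No limit | None specific to blood ketones in this range | Stricter than the blood-ketone rule |
| 3. Glucose raised after a recent meal | Test ketones | No test required | Section 8.7 signal 2 has no meal exemption | Stricter than the blood-ketone rule; agrees with section 8.7 |
| 4. Positive urine test | No vigorous activity | Not addressed | Section 2.2 lists urine ketones under severe hyperglycemia; exercise suspended | Weaker |
| 5. No ketones, feels well | Exercise is fine | Exercise allowed | None | Same |

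Three points follow.

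1. Case 1 is the main fault. The protocol bars exercise of any intensity and tip B bars only the vigorous kind. If ketones reach 1.0 mmol/L after a recent meal, section 2.2's meal condition removes its rule, but signal 1 has no such condition, so tip B is still weaker than section 8.7.
2. Case 4 is a smaller fault of the same type. It rests on reading the severe-hyperglycemia definition as a list of alternatives, so that urine ketones alone are enough.
3. In case 2, tip B is stricter only than the blood-ketone rule. Someone with blood ketones below 1.0 mmol/L and a positive urine test falls under the severe-hyperglycemia text, which is tighter than tip B.

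Next, would daily review catch the problem? Section 2.2 sets that review for "each of the first 14 days of the trial for each participant", and the section 8.7 heading also says two weeks. The app runs from nominal Day 22 to Day 50. Fourteen days counted from consent end on Day 14, from device set-up on Day 21 (8 + 13), and from the start of the intervention on Day 35 (22 + 13). On any of these counts, part or all of the app period lies outside the window. Tool #2 does mention staff checking the dashboard daily for safety under the monitoring plan, but it does not say whether the formal response extends beyond two weeks.

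**The case against.** The strongest reply is that tip B is only a reminder. Table 3 is titled as an example. Participants learn the stop rule before any weekly report exists: section 2.2 gives the 1.0 mmol/L limit as a worked instance of their education, and the exercise physiologist covers safety at Visit 4 using Appendix 22a. The study supplies a blood ketone meter. Daily dashboard checks for Tool #2 may well continue throughout app use. Section 8.7, Tracking B, adds a two-weekly review by the principal investigator and a study endocrinologist that names this very pattern.

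All of this stands, and it lowers the risk. It does not correct the text. Tip B is the only wording the protocol gives for this pattern. If the handout states the stricter rule, participants hold two written instructions that disagree.

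Some stronger readings are tempting, and the documents do not support them:

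- *Tip B tells people to exercise with ketones.* It does not; it clears exercise only when there are none. The fault is an omission.
- *Tip B should be replaced by the section 2.2 wording.* That would bring in a meal exemption that signal 2 lacks, and would drop the caution below 1.0 mmol/L.
- *The urine option should go, because the mailed kit lists no urine strips.* Section 2.2 includes urine ketones in participant education, so removing them only from tip B would create a new mismatch.
- *A light session with high ketones means certain removal.* Section 2.2 says removal will follow a ketoacidosis episode not closely related to pump site failure, whereas section 6.5 says researchers may withdraw the participant.
- *The number of weekly reports measures exposure.* Only reports showing a start above 270 mg/dL carry tip B.

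**Conclusion.** The point holds in a narrow form. Tip B is weaker than the protocol at blood ketones of 1.0 mmol/L or more and after a positive urine test. In neither case does it state that exercise should not take place. It is stricter than section 2.2's blood-ketone rule, though not than the severe-hyperglycemia text, for detectable blood ketones below 1.0 mmol/L. It is also stricter than the blood-ketone rule on recent meals.

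The number of people affected cannot be estimated. The documents name the high-glucose start as one of the more common patterns but give no rate for it, and none for positive ketones. Appendix 22a was not available, so what participants are told there is unknown.

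This is a minor safety-wording correction. It is worth making because the text concerns ketoacidosis and reaches participants directly. No endpoint, sample size or analysis is affected.

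**What to change.** Replace the middle sentence of tip B with: *Do not exercise if your blood ketones are 1.0 mmol/L or higher, or if a urine ketone test is positive; contact your diabetes provider. If blood ketones are detectable but below 1.0 mmol/L, avoid vigorous activity.*

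Keep the rest of tip B. The ketone test without a meal exemption matches signal 2 in section 8.7, and the urine option matches the education described in section 2.2. The study physicians should confirm the instruction below 1.0 mmol/L, since section 2.2's blood-ketone rule is silent there. Check that the Appendix 22a handout says the same.

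The cost is two sentences in the report template and the protocol, plus the IRB amendment that section 9.1 requires for any protocol change.
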